12.5. Data management

The trial statistician will continuously monitor eCRFs for accuracy and completeness (including range and logical checks) and for compliance with this protocol. Any inaccuracies, inconsistencies, or deviations will be reported to the appropriate study center, with a request for a correction or an explanation. The trial database will be backed up regularly. The sponsor/coordinating investigator may also appoint staff to conduct on-site monitoring to verify eCRFs with source documents. A detailed plan for data management has not been developed at the time of writing, but it will be attached to the Clinical Study Report.

13. Statistical Analysis

Statistical analyses will be performed using the latest version of R software. All statistical hypothesis tests that can be two-sided will be two-sided. P-values <0.05 will be considered statistically significant, unless otherwise specified. P-values will be rounded to two decimal places if ≥ 0.01 and rounded to three decimal places if <0.01 but ≥ 0.001 . P-values <0.001 will be expressed as " <0.001 ".

The zoledronic acid and placebo groups will be defined according to randomization. Baseline date will be defined as the date of randomization. Follow-up time will be defined as the date of death, withdrawal, loss to follow-up, or last follow-up contact (whichever came first) minus the date of randomization plus 1 day (to account for the possibility of an event later in the day of randomization). Incomplete follow-up will be defined as follow-up time that ends before the last study contact.

Study Name: The Fragility Fracture Trial
Version No: 2
Date: 2020-10-04
EudraCT No: 2019-004766-17

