13.8. Subgroup, sensitivity, and exploratory analyses

Baseline characteristics and efficacy outcomes will be presented in subgroups defined by type of baseline fragility fracture (grouped by the first 3 characters of ICD-10-SE codes), age (65-74, 75-84, or ≥ 85 year), sex, study center, and FRAX 10-year probability of major osteoporotic fracture. In the efficacy analysis, product terms will be included in regression models to assess interaction of treatment with time since fragility fracture, type of fragility fracture, age, sex, study center, physical activity (mean steps/day), and receipt of one or both infusions. These interaction effects will be tested using Wald tests for numeric and binary variables and likelihood ratio tests for multi-level categorical variables. We do not expect these interaction analyses to show significant differences in effect.

Six sensitivity analyses will be conducted. First, to assess the presence of confounding, regression analyses will be adjusted for the following baseline covariates: age, sex, BMI, study center, time since fragility fracture, and site of fragility fracture (grouped by the first 3 characters of ICD-10-SE code). Second, the efficacy analysis will be rerun in a per-protocol population (i.e., participants who met all eligibility criteria, either died or completed follow-up, and both were qualified to receive and did receive the 2 assigned infusions). Third, efficacy concerning time-to-event outcomes will be analyzed using the Andersen-Gill Cox model for recurrent events.⁶³ Fourth, in the analysis of the primary outcome, the potential effect of informative censoring (including the competing risk of death) will be assessed by rerunning Cox models under the extreme scenarios that all participants who did not complete follow-up either (1) sustained a fracture at the time of censoring (i.e., were at high risk of fracture) or (2) had complete follow-up with no event (i.e., were at low risk of fracture).⁶⁴ Fifth, participants with a history of cancer at baseline will be excluded from the efficacy analysis of new cancers diagnosed during follow-up. Sixth, outcome events not verified by medical records will be included in the efficacy analyses.

Study Name: The Fragility Fracture Trial
Version No: 2
Date: 2020-10-04
EudraCT No: 2019-004766-17

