13.10. Sample size and power calculations

The trial will enroll 2900 patients, of whom 227 will need to sustain a clinical fracture during follow-up for the study to achieve 90% power to detect a 35% reduction in clinical fractures with the log-rank test (2-sided significance level of 5%). This calculation assumes a 4-year fracture risk of 10% in the placebo group and an overall dropout rate of 5% (due to withdrawal or loss to follow-up, i.e., deaths excluded). The details of the calculation can be found in Appendix 1. Appendix 2 provides a table of required sample sizes under varying assumptions. As shown, the required sample size is sensitive to changes in the assumed hazard ratio and the assumed fracture risk in the placebo group, but it is relatively insensitive to changes in the dropout rate.

To put the assumptions of the sample-size calculation in perspective, we note that 3 of 4 previous large trials of zoledronic acid had 90% power,^{19,20,22} whereas the fourth had 80% power.²¹ Incomplete follow-up (deaths excluded) was observed in 4% of women with osteopenia (6-year follow-up),²¹ 8% of men with osteoporosis (1-year follow-up),²² 13% of women with osteoporosis (3-year follow-up),¹⁹ and 17% of hip fracture patients (1.9-year

Study Name: The Fragility Fracture Trial
Version No: 2
Date: 2020-10-04
EudraCT No: 2019-004766-17

median follow-up).²⁰ Three of the trials that were powered to demonstrate effects on clinical fractures, and these showed effects of 27%,²¹ 33%,¹⁹ and 35%.²⁰

The assumed 4-year fracture risk of 10% was derived from data about the Swedish population that we have previously collected from the Swedish National Patient Register. We selected adults in Sweden who were aged 65 to 85 years and who suffered an initial fracture of the arm or lower leg in 2006 (ICD-10-SE codes: S42, S52, or S82). There were 10,361 such individuals who were not prescribed bone-protective treatment over the next 4 years. Their mean age was 74.9 years and 73% were women. Over the 4 years, 10.0% (n=1028) suffered a new fracture at a different skeletal site. We expect the restriction of the analysis to fractures of a different skeletal site to lead to an underestimation of the incidence of new fractures, but the restriction is necessary to avoid counting the same fracture twice. The distribution of fractures by skeletal site was as follows:

1. 457 fractures of the hip
2. 148 fractures of the upper arm
3. 125 fractures of the lower leg and foot joint

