- 72 International Conference on Harmonisation of Technical Requirements for Registration of Pharmaceuticals for Human Use. ICH harmonised tripartite guideline E3: structure and content of clinical study reports. 1995.
- 73 International Committee of Medical Journal Editors. Recommendations for the conduct, reporting, editing, and publication of scholarly work in medical journals. 2016.
- 74 Williamson S, Landeiro F, McConnell T et al. Costs of fragility hip fractures globally: a systematic review and meta-regression analysis. *Osteoporos Int* Osteoporosis

Study Name: The Fragility Fracture Trial
Version No: 2
Date: 2020-10-04
EudraCT No: 2019-004766-17

- International, 2017;28:2791–2800.
- 75 Schoenfeld D. Sample-size formula for the proportional-hazards regression model. *Biometrics* 1983;39:499–503.
- 76 Freedman LS. Tables of the number of patients required in clinical trials using the logrank test. *Stat Med* 1982;1:121–129.

Study Name: The Fragility Fracture Trial
Version No: 2
Date: 2020-10-04
EudraCT No: 2019-004766-17

19. Appendix 1: Sample Size Calculation

The first step in the sample size calculation is to calculate the number of fractures that need to be observed in the trial, because the log-rank test is powered by events rather than participants. According to Schoenfeld,⁷⁵ the necessary number of fractures (assuming 90% power, a 2-sided alpha of 5%, and a hazard ratio of 0.65) is

$$\frac{4(Z_{1-0.05/2} + Z_{0.90})^2}{\ln(0.65)^2} = 227.$$

Here, z_p is the p^{th} quantile of the standard normal distribution and $\ln(\cdot)$ is the natural logarithm.

The second step is to estimate the required number of participants, ignoring any early dropouts due to withdrawal. According to Schoenfeld,⁷⁵ a 10% fracture risk in the placebo group and a hazard ratio of 0.65 corresponds to an estimated risk of

$$1 - (1 - 0.10)^{0.65} = 0.06619$$

in the zoledronic acid group. With 227 fractures, the required number of participants becomes

$$\frac{227}{(0.10 + 0.06619)/2} = 2732.$$

The third step is to adjust the sample size of 2732 for dropouts. As suggested by Freedman,⁷⁶ this can be done simply by dividing the sample size by the proportion of non-dropouts:

$$\frac{2732}{1 - 0.05} = 2876.$$

For simplicity, we round this number up to 2900.

Study Name: The Fragility Fracture Trial
Version No: 2
Date: 2020-10-04
EudraCT No: 2019-004766-17

20. Appendix 2: Sample Sizes Under Varying Assumptions

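### The informative-censoring sensitivity analysis treats both arms alike and codes deaths as fractures in one scenario, so it does not bound arm-differential bias

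*Protocol*

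**What the plan says.** Section 13.8 lists six sensitivity analyses. The fourth concerns the primary outcome, and its stated aim is that "the potential effect of informative censoring (including the competing risk of death) will be assessed". The method is "rerunning Cox models under the extreme scenarios that all participants who did not complete follow-up either (1) sustained a fracture at the time of censoring" or (2) had full follow-up without an event. Neither scenario distinguishes the arms or the reasons for leaving.

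Who is affected follows from the opening of Section 13. Follow-up ends at death, withdrawal, loss or last contact, whichever comes first, and "Incomplete follow-up will be defined as follow-up time that ends before the last study contact". A death before 48 months is therefore incomplete follow-up. Two other places agree: Section 13.4 names death among the causes of not completing follow-up, and the per-protocol definition in Section 13.8 lists dying and completing as alternatives.

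Section 13.6 decides efficacy on the log-rank test. No decision rule is attached to the sensitivity analyses.

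**The concern.** Bias in a hazard ratio from censoring depends on how the people who leave differ between the arms. A scenario in which all of them fracture, and one in which none does, are extremes for the overall fracture risk but not for the treatment contrast. If treated leavers were at high risk and placebo leavers at low risk, or the reverse, neither scenario would represent it.

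Separately, scenario 1 becomes a composite of fracture, death and dropout. Exits that treatment does not affect pull a real fracture effect toward 1. If treatment lowers mortality, which Section 3.2 makes a secondary objective, that effect would show up in scenario 1 as fewer fractures.

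The stake is the robustness statement in the report: it could suggest fragility or support for reasons that have little to do with informative censoring of fractures.

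**Working it through.** **Inputs from the protocol.** Section 13.10 gives 2900 patients, 10% placebo fracture risk over 4 years and 5% dropout ("due to withdrawal or loss to follow-up, i.e., deaths excluded"); Section 10 gives 1:1 allocation. Section 13.10 states "of whom 227 will need to sustain a clinical fracture during follow-up", and Appendix 1 computes this "assuming 90% power, a 2-sided alpha of 5%, and a hazard ratio of 0.65".

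**The plan's own figures reproduce.** Schoenfeld's formula gives 227 events. Treated risk is 1 − 0.9^0.65 = 0.06619. Then 227 / ((0.10 + 0.06619)/2) = 2732, and 2732/0.95 = 2876, rounded up to 2900.

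**Assumed.** The protocol gives no 4-year mortality, so a range of 0 to 15% is used. Times to fracture, death and dropout are independent and exponential.

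**Step 1: dilution in scenario 1.** The 4-year cumulative hazards are:
- placebo fracture: F = −ln(0.90) = 0.1054
- treated fracture: 0.65F = 0.0685
- dropout: W = −ln(0.95) = 0.0513
- death: M = −ln(1 − mortality)

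Every exit becomes an event in scenario 1, so its hazard ratio is (0.65F + W + M) / (F + W + M).

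| Assumed mortality | M | Calculation | Scenario 1 HR | Real / imputed fractures (simulated) | Scenario 1 significant (simulated) |
|---|---|---|---|---|---|
| 0% | 0 | 0.1198/0.1567 | 0.76 | 236 / 139 | 72% |
| 5% | 0.0513 | 0.1711/0.2079 | 0.82 | 230 / 270 | 58% |
| 10% | 0.1054 | 0.2251/0.2620 | 0.86 | 225 / 402 | 46% |
| 15% | 0.1625 | 0.2823/0.3192 | 0.88 | 219 / 534 | 38% |

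Simulated mean hazard ratios agree to within 0.01 (0.77, 0.82, 0.86, 0.89). The main analysis stays at 0.65 and is significant in 88 to 90% of trials; scenario 2 also stays at 0.65. Of trials with a significant main result, scenario 1 loses significance in 20% with no deaths and in 48% at 10% mortality.

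**Step 2: a mortality benefit read as a fracture benefit.** Take no fracture effect and an assumed death hazard ratio of 0.72. Scenario 1 gives (F + W + 0.72M) / (F + W + M):
- 10% mortality: 0.2325/0.2620 = 0.89, significant in about 31% of simulated trials
- 15% mortality: 0.2737/0.3192 = 0.86, significant in about 54%

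The main analysis is significant in about 5%. With a weaker death hazard ratio of 0.85 at 10% mortality, scenario 1 gives 0.2462/0.2620 = 0.94.

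**Step 3: reasons for leaving that differ by arm at equal rates.** Take a true hazard ratio of 1, no deaths and 5% withdrawal in each arm (about 72 people). Suppose 30% of the treated participants who would have fractured leave first (0.30 × 145 ≈ 43), and no such placebo participant does.
- Main analysis: about 102 against 144.5 fractures, HR 0.70, significant in 85%.
- Scenario 1: crude ratio (102 + 72)/(144.5 + 72) = 0.80, simulated HR 0.79, significant in 67%.
- Scenario 2: HR 0.70, significant in 85%.

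The two scenarios span 0.70 to 0.79 and miss the true value of 1. If 20% leave first, the main HR is 0.80, scenario 1 gives 0.86 and scenario 2 gives 0.80, which again excludes 1.

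**Step 4: unequal exit rates.** With 10% mortality in both arms, a true HR of 0.65 and dropout of 10% on treatment against 5% on placebo, scenario 1 gives (0.0685 + 0.1054 + 0.1054)/(0.1054 + 0.0513 + 0.1054) = 1.07; scenario 2 gives 0.64. So scenario 1 does react to unequal rates, although here it lands far from the truth.

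**The case against.** A fair defence has five parts.

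- **The analysis is not blind.** A reader might infer that it cannot detect informative censoring at all. Step 4 shows otherwise, and Section 13.4 also compares follow-up duration between arms and reports non-completion by cause. This stands. The gap is narrower: leaving for different reasons at similar rates, which a comparison of durations need not reveal.
- **Deaths are relabelled in scenario 1 only.** Scenario 2 keeps the dead event-free in the risk set, much as a subdistribution-hazard analysis would, and its stability is no fault in itself. This stands, although scenario 2 treats withdrawn participants in the same way.
- **No efficacy finding is overturned.** A reader might infer that scenario 1 could reverse a positive trial. Section 13.6 does not support that, and Section 13.8 itself calls the scenarios extreme.
- **Design limits the problem.** Follow-up continues after treatment stops (Section 6.1), those wishing to withdraw may stop treatment only (Section 15.4), and the Swedish Fracture Register is searched for consenting participants (Section 7.1). This lowers the number of leavers. Even so, Section 13.10 plans for 5% dropout and cites 4 to 17% incomplete follow-up in earlier trials.
- **The sizes rest on assumptions.** Mortality is not given, and Step 3 is a strong mechanism: about 43 of 72 treated leavers (60%) would have fractured. Both are true. With no deaths at all, however, dilution to about 0.77 remains.

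Detail could be left to a statistical analysis plan, but the protocol already fixes a specific method, and that method is what is questioned here.

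**Conclusion.** The point holds as a cheap improvement to a supportive analysis. Applying one assumption to both arms does not bound bias from arm-differential reasons for leaving when exit rates are similar. Scenario 1 additionally mixes death with fracture. At 5% dropout and an assumed mortality of 0 to 15%, it moves a true hazard ratio of 0.65 to between about 0.77 and 0.88. It can also turn a pure mortality benefit into an apparent fracture benefit; the size of that depends on the assumed mortality and death hazard ratio. Scenario 2 remains close to the main result. The primary test and the sample size are unaffected; what suffers is the conclusion about robustness.

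**What to change.** Rewrite the fourth sensitivity analysis before unblinding.

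1. Separate deaths from withdrawal and loss to follow-up. Treat death as a competing event, for example by reporting cause-specific hazards for fracture and for death and a subdistribution hazard ratio for fracture. Do not count a death as a fracture.
2. For withdrawal and loss only, replace the two same-direction scenarios. Impute the unobserved time with the fracture hazard multiplied by a factor delta, varied independently by arm, and report the combinations at which significance is lost (the tipping point).
3. Keep the imputation graded. If every treated leaver fractures and no placebo leaver does, a true HR of 0.65 becomes 1.17 at 5% dropout, so that single worst case would fail at the planned dropout rate and tell the reader little.

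The cost is revised wording, some programming and one extra table; no new data are needed.

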3.3. Exploratory objectives

The exploratory objectives are as follows:

1. To investigate whether the effect of zoledronic acid on new clinical fracture decreases with age
2. To investigate the time-to-onset of effect of zoledronic acid on clinical fractures
3. To investigate whether a higher level of physical activity leads to a greater reduction in clinical fractures with zoledronic acid
4. To investigate whether zoledronic increases muscle strength, as compared with placebo
5. To investigate whether the effect of zoledronic acid on new clinical fractures is greater in participants who have a higher 10-year probability of major osteoporotic fracture according to the FRAX fracture risk assessment tool
6. To investigate whether zoledronic acid reduces height loss, as compared with placebo
7. To investigate whether zoledronic acid improves health-related quality of life
8. To investigate whether zoledronic acid reduces the risk of death, cancer, clinical fractures, and cardiovascular disease, as compared with placebo, over 10 years

Efficacy by age was selected as an exploratory objective because some researchers suggest that bone-protective therapy is less effective in the oldest age groups, perhaps because the high incidence of falls offsets beneficial skeletal effects.^{32,33} Low treatment rates of osteoporosis have also been observed in the oldest age groups.³⁴ Efficacy by level of physical activity was selected because it is well known that bone-protective agents have different effects on bone mineral density in different individuals. Given that physical loading decreases the risk of fractures and is necessary for maintaining bone health at all ages,³⁵ we hypothesize that zoledronic acid will result in a greater increase in bone density, and therefore a greater decrease in fracture risk, in participants who are physically active. Muscle strength is included as an explanatory outcome because it is a possible mechanism for a beneficial effect of zoledronic acid on falls. This mechanism is supported by the known crosstalk between osteocytes and muscle cells, which is mediated by pathways influenced by bone-protective

Study Name: The Fragility Fracture Trial
Version No: 2
Date: 2020-10-04
EudraCT No: 2019-004766-17

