To assess the time-to-onset of treatment effect on the primary outcome, Kaplan-Meier curves will be compared using the log-rank test with censoring at months 48, 42, 36, and so on until month 6. To avoid the problem of multiple testing, a fixed-sequence procedure will be used in which the test will first be performed for risk at month 48, then at month 42, and so on until month 6.⁶⁵ If a p-value ≥ 0.05 is obtained, the results of all subsequent tests will also be considered non-significant. Similarly, Cox regression will be used to estimate hazard ratios and 95% confidence intervals, with censoring at month 48, 42, and so on until month 6.

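### The gated, cumulative log-rank tests planned for time to onset show when enough fractures have accrued, not when the effect begins

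*Protocol*

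**What the plan says.** Protocol section 3.3 lists as exploratory objective 2: "To investigate the time-to-onset of effect of zoledronic acid on clinical fractures". Section 13.8 gives the analysis and names onset of the effect on the primary outcome as its purpose. The method is this: "Kaplan-Meier curves will be compared using the log-rank test with censoring at months 48, 42, 36, and so on until month 6". The order is backward: "a fixed-sequence procedure will be used in which the test will first be performed for risk at month 48, then at month 42". Once a p-value of 0.05 or more appears, "the results of all subsequent tests will also be considered non-significant". Cox hazard ratios with 95% confidence intervals are estimated at the same censoring times.

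Two other places bear on the point. Section 13.6 plans log-minus-log plots and a Wald test of treatment-by-time terms, with hazard ratios by interval (for example 6 or 12 months) only if proportional hazards is clearly violated. Section 13.10 sizes the trial for the full 48-month comparison alone: "227 will need to sustain a clinical fracture during follow-up for the study to achieve 90% power to detect a 35% reduction". The protocol gives no power for any earlier cut-off.

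**The concern.** Each truncated test uses all data from randomization to its cut-off, so an earlier cut-off always has fewer fractures. If the drug works equally well from day 1, the tests still lose significance as the cut-off moves back, because power falls. The earliest month that survives the gate therefore measures event accrual, and it would move earlier in a larger trial with the same drug effect.

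The hazard ratios reported beside the tests help only in part. The one censored at month 6 is a genuine estimate for months 0 to 6. Those at later cut-offs blend early and late periods. The interval estimates of section 13.6 that would separate them appear only after a clear proportional-hazards violation, which an immediate and constant effect should not trigger.

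The answer to one exploratory objective is at stake. A published onset month of, say, 18 could be taken as a property of zoledronic acid when it reflects the number of fractures.

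**Working it through.** **Inputs from the protocol (sections 10, 13.8, 13.10, Appendix 1).** 2900 participants allocated 1:1; 4-year placebo risk 10%; hazard ratio 0.65; dropout 5%; two-sided 5% level; cut-offs at months 48, 42, ..., 6.

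**Assumptions, not in the protocol.** Fracture hazard constant over the 48 months (varied below); dropout spread evenly over follow-up; hazard ratio 0.65 from day 1.

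**Step 1: the protocol's own figures.** 4(1.960 + 1.282)² / (ln 0.65)² = 226.5, so 227 events. Risk on zoledronic acid = 1 − 0.90^0.65 = 0.06619. 227 / ((0.10 + 0.06619)/2) = 2732, and 2732/0.95 = 2876, rounded to 2900. All reproduce.

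**Step 2: events and power by cut-off.** The placebo hazard is −ln(0.90)/48 = 0.002195 per month, and 0.65 times that on zoledronic acid. Power = Φ(√(D/4) × |ln 0.65| − 1.96), with |ln 0.65| = 0.431. For month 6, D is about 31, so √(31/4) × 0.431 − 1.96 = −0.76 and power is about 22%.

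| Cut-off (month) | Expected events D | Power |
|---|---|---|
| 6 | 31 | 22% |
| 12 | 62 | 40% |
| 18 | 92 | 54% |
| 24 | 122 | 66% |

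Removing all dropouts at day 0 instead gives 30, 59, 88 and 117 events and power of 22%, 38%, 52% and 64%. The conclusion is the same.

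**Step 3: the whole backward sequence, simulated.** This used 20,000 trials with an immediate, constant hazard ratio of 0.65. The earliest month still significant was:

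| Month 6 | 12 | 18 | 24 | 30 | 36 | 42 | 48 | None |
|---|---|---|---|---|---|---|---|---|
| 15% | 17% | 16% | 13% | 11% | 8% | 6% | 5% | 9% |

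Among trials significant at month 48, 83% show month 12 or later and 65% show month 18 or later. The median is month 18.

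**Step 4: sensitivity.** Section 5.1 says refracture risk is highest soon after the initial fracture. Section 13.10 expects its register figure to understate new fractures, and Appendix 2 also tabulates 15% placebo risk. The share showing month 12 or later, among trials significant at month 48, is:

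| Hazard shape | Placebo risk 10% | Placebo risk 15% |
|---|---|---|
| Constant | 83% | 74% |
| Weibull shape 0.7 (moderate front-loading) | 67% | about 50% |
| Weibull shape 0.5 (strong front-loading) | 50% | 32% |

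**Step 5: how well an early period can be estimated.** With 31 events in months 0 to 6, the standard error of the log hazard ratio is about 2/√31 = 0.36. The interval around 0.65 is 0.65 × exp(±1.96 × 0.36), or about 0.32 to 1.31.

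**Step 6: power of an early-versus-later comparison.** Suppose the true hazard ratio is 1 up to month 6 and 0.65 afterwards. About 38 events fall before month 6 and 203 after. The standard error of the difference in log hazard ratios is √(4/38 + 4/203) = 0.354, and power is Φ(0.431/0.354 − 1.96), about 23%. For a 12-month delay the same calculation gives about one third.

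**The case against.** A reader might infer that the protocol states a rule equating onset with the earliest significant month, and that the rule always gives a wrong answer. The text does not support that. Section 13.8 says only which tests count as significant. The sequence can also be read as asking by which month a cumulative benefit has been shown. For that question the backward gate is valid and controls type I error across cut-offs. This stands, but the analysis is introduced as an assessment of time to onset and no other rule is given, so the earliest significant month remains what most readers would take from it.

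It is also tempting to say that none of the planned hazard ratios isolates the early period. That is wrong for the estimate censored at month 6, which uses only months 0 to 6, so an early value near 0.65 would be visible. Section 13.6 also already tests whether the effect changes with time. What is missing is unconditional estimates for the later periods and a statement of how onset will be read.

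Finally, the size depends on a constant hazard that the protocol does not assume. Front-loading or a higher placebo risk brings events forward and weakens the problem. With both, in their stronger form, most trials significant at month 48 would reach month 6. So the claim that an immediate effect would usually look delayed holds only in some of these scenarios.

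**Conclusion.** The concern holds in this limited form. The tests in section 13.8 cannot date onset, because the earliest significant cut-off tracks accumulated events. With an immediate hazard ratio of 0.65, the protocol's sample-size inputs and a constant hazard, about 83% of trials significant at month 48 would show month 12 or later, with a median of 18. Across the hazard shapes and placebo risks examined, the share runs from 83% down to 32%. Even the lowest figure means about one trial in three would suggest a delay that does not exist. The analysis is exploratory, so the primary and secondary conclusions and the sample size are untouched. The change is still worth making, because it is cheap and prevents a specific misreading.

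**What to change.** In section 13.8:

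- Report unconditionally the treatment hazard ratio with 95% confidence interval in pre-specified periods, for example 0–6, 6–12, 12–24 and 24–48 months.
- Present beside them the treatment-by-time test already planned in section 13.6, and the Kaplan-Meier risk difference over time with pointwise 95% confidence intervals.
- State that onset will not be dated from the earliest significant log-rank test. The gated tests may stay, but only to say by which month a cumulative benefit has been demonstrated.
- Do not substitute a rule that calls onset delayed only if early and later hazard ratios differ. With about 23% power for a 6-month delay and about one third for a 12-month delay, it would usually miss a real one.

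The cost is a few sentences and a few lines of code, with no new data. The downside is wide early intervals (about 0.32 to 1.31 for months 0 to 6), so the trial may have to report that onset cannot be dated.
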